#### Risk management of malaria infection

The number of viable blood stage parasites used to infect the subjects in this study (~2,800) is substantially lower than the parasitaemia reached after the bite of a single malaria-infected mosquito, where approximately 30,000 parasites are released into the blood when they break out of a single infected liver cell [36]. In this study, parasite growth and malaria symptoms will be closely monitored in subjects following administration of the challenge agent. The threshold for commencement of antimalarial drug treatment defined for this study (Day 8) has been selected since it is prior to the time point at which advanced clinical symptoms of malaria are likely to occur, as observed in the previous 25 clinical trials performed with the 3D7 challenge agent.

#### Risk management of liver function abnormalities

Transient, asymptomatic liver function test (LFT) abnormalities including rare cases of alanine aminotransferase (ALT) and aspartate aminotransferase (AST) elevations >10 fold the upper limit of normal (xULN) have been reported in several subjects in IBSM studies [35, 37]. However, no changes in bilirubin were reported except for in one subject with unappreciated existing liver disease [35, 37]. The LFT derangements did not require treatment, and resolved by the end of the studies. A few cases of the LFT elevations were considered serious AEs (SAEs) by two Pharma sponsors due to internal processes for SAE notifications. Following an independent review involving independent liver injury experts, it was found that these LFT elevations are most likely a direct consequence of the malaria infection, rather than reflecting a direct drug-induced liver injury caused by an investigational antimalarial drug. As a precaution all subjects in this study will undergo regular

safety monitoring to assess for asymptomatic LFT abnormalities. Subjects are required to abstain from the intake of possibly hepatotoxic substances such as alcohol and paracetamol during the course of the study (see Sections 5.2 & 7.6). Drugs of abuse are not permitted under any circumstance.

#### Risk management of cardiac AEs

To our knowledge, cardiac SAEs have been reported in healthy subjects in the Netherlands participating in malaria challenge studies using sporozoites i.e. direct feeds by infected mosquitoes rather than IBSM infection. Refer to the P. falciparum 3D7 Investigator's Brochures for further details [35]. No cardiac SAEs caused by the inoculum have been reported in IBSM studies. As a precaution, people at significant risk of cardiovascular disease will be excluded from participating in IBSM studies, and regular safety monitoring including physical examination and electrocardiogram (ECG) recordings will take place for all subjects.

#### Investigational Medical Product (IMP) risks

##### OZ439 risks

To date, OZ439 administered either as a monotherapy or in combination with a partner anti-malarial, has been generally well tolerated in malaria patients and healthy subjects. In a monotherapy Phase IIa study of OZ439 doses of 200, 400, 800 and 1200 mg in malaria patients, increased blood creatine phosphokinase was the most frequently reported AE; a dose relationship was not seen for this AE and no clinically relevant muscular AEs were reported. Gastrointestinal (GI) AEs, including vomiting, abdominal pain, diarrhea and nervous system disorders, including dizziness and headache, were reported more frequently with 1200 mg OZ439 compared to the other dose cohorts. None of these AEs were SAEs.

One case of vasovagal syncope considered related to therapy was reported in association with sinus arrest and orthostatic hypotension. Two SAEs of atrial fibrillation were reported in healthy volunteers. One case occurred at day 35 post dose and was considered not related to the study drug. The second case was moderate atrial fibrillation, considered possibly related to the study drug in a subject who had received OZ439 and FQ. The event occurred in context of symptomatic orthostatic hypotension and resolved spontaneously without medical treatment.

In a Phase IIb study, where OZ439 was evaluated in combination with PQP, in patients with uncomplicated P. falciparum malaria, malaria and electrocardiogram (ECG) QTc prolongation were the most frequently reported AEs. Malaria was reported with a higher incidence in the OZ439 800 mg:PQP 960 mg and in the OZ439 800 mg:PQP 640 mg treatment arms than in the OZ439 800 mg:PQP 1440 mg treatment arm. The ECG QTc prolongation was reported with a higher incidence in the OZ439 800 mg:PQP 1440 mg and the OZ439 800 mg:PQP 960 mg treatment arms than in the OZ439 800 mg:PQP 640 mg treatment arm. Concentration-related QTc prolongation

has been widely documented with PQP. Diarrhea and vomiting were the most frequently reported AEs of the GI system in patients treated with both OZ439 and PQP. None of these AEs were SAEs.

The AE profile for OZ439 in healthy subjects was similar to the AE profile in malaria patients. Gastrointestinal AEs, including nausea, vomiting, and diarrhea, were the most frequently reported AEs in healthy subjects treated with OZ439 alone or OZ439 in combination with either PQP, MQ, or FQ. A tendency for a dose-response relationship was seen for GI events. These AEs were generally mild in intensity.

Eight subjects treated with OZ439, including 6 malaria patients and 2 healthy volunteers, have had SAEs, including *P. vivax* relapse, pyelonephritis, increased alanine aminotransferase (ALT), increased aspartate aminotransferase (AST), decreased neutrophil, anemia, febrile convulsion and decreased hemoglobin in malaria patients; and atrial fibrillation and a gunshot wound in healthy subjects. Five AEs reported in malaria patients (increased ALT, increased AST, decreased neutrophil count, anemia and decreased hemoglobin) were assessed as related to study drug by the investigator.

An AE of vomiting led to study drug discontinuation in 1 malaria patient treated with OZ439. Ten healthy subjects treated with OZ439 discontinued a Phase Ia study due to an AE. Vomiting (5 subjects) was the most frequently reported AE leading to study discontinuation in the 10 healthy subjects. Except for a few cases observed with  $\alpha$ -tocopherol polyethylenglycol 1000 succinate (TPGS) formulation, vomiting is not reported in healthy subjects at doses < 800 mg OZ439.

No Hy's law cases have been observed. However, mild to severe and reversible increases in ALT and AST were seen in OZ439-treated malaria patients; these increases did not appear to be dose dependent. Decreases in hemoglobin, neutrophils, and platelets were also seen in OZ439 malaria patients; however, these decreases were consistent with those observed in acute malaria. Close monitoring of liver function is required in the clinical studies.

In the clinic, a significant effect on placebo-corrected change from baseline QTcF was not demonstrated for OZ439. In healthy subjects the effect of OZ439 alone on QTc was minimal, with a maximum mean QTcF increase from baseline and placebo of 8.5 (Study MMV\_OZ439\_12\_002). In Study MMV\_OZ439\_12\_003, 1 healthy subject with an undisclosed history of mitral and tricuspid regurgitation was discontinued from the study due to asymptomatic supraventricular/junctional tachycardia after dosing with 120 mg OZ439. QTc prolongations (both QTcB and QTcF) were seen when OZ439 was administered in combination with PQP to malaria patients and healthy subjects. Most of the prolongations were in the range of >30 ms but <60 ms; however, prolongations >60 ms were observed in malaria patients, with QTcF values that exceeded 500 ms in 2 patients (1 hypokalemic patient). Reversible right bundle branch block (3 patients), reversible first degree atrioventricular block (1 patient), and a mild reversible

sinus bradycardia (1 patient) were also observed in malaria patients treated with OZ439. Close monitoring of cardiac function is required in the clinical studies.

In healthy subjects treated with OZ439 alone or OZ439 in combination with PQP, gastrointestinal (GI) symptoms which include nausea, vomiting, and diarrhea, are the most commonly reported AEs and these AEs have been reported to be generally mild in intensity. OZ439 was clinically well tolerated in two previous IBSM studies (QP12C10 and QP14C12) where the highest dose tested was 500 mg. In a Phase I IBSM study QP12C10 in healthy subjects infected with *P. falciparum*, most of the AEs reported were assessed as probably related to the inoculum (i. e., malaria). There were no events considered probably related to OZ439. In another Phase I IBSM study QP14C12, healthy subjects infected with *P. falciparum* received OZ439 in combination with another investigational antimalarial, DSM265. No new clinically relevant safety signals were observed. OZ439 may be contraindicated in persons with known hypersensitivity to artemisinin compounds or to any components of the product formulation. Carcinogenicity studies have been performed with OZ439. OZ439 has shown in vivo embryofetal toxicity in the rat. Therefore, OZ439 should not be administered to pregnant or breastfeeding women. However, OZ439 can be administered to women of child bearing potential (WOCBP) with use of a strict double method of contraception in well controlled clinical trials and under medical supervision. Healthy male and female subjects participating in studies of OZ439 must agree to use a double method of contraception for a duration defined in section 5 (Inclusion criteria) of this protocol.

No deaths have been reported in any of the clinical studies.

Additional information on nonclinical and clinical studies conducted with OZ439 is provided in the IB [38].

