### Vital signs

Vital signs (temperature, heart rate, respiratory rate and blood pressure) will be measured at screening after the subject has rested in the supine position for at least 5 minutes and in the standing position within 23 minutes when changing from the supine to standing position (blood pressure and heart rate only). At all other time points, vital signs will be measured after the subject has rested in the seated position for at least 5 minutes. Tympanic temperature will be taken at the clinical unit

The normal ranges for vital signs on study are:

Parameter	Range
Systolic blood pressure	90-140mmHg
Diastolic blood pressure	50-90 mmHg
Heart rate	50 -100 bpm
Temperature	35.0-37.5°C
Respiratory rate	10-25 breaths/min
Peripheral O2 Saturation	>=95%

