### Biochemistry and CRP biomarker

Sodium (SODIUM)	Alkaline phosphatase (ALP)
Potassium (K)	Alanine aminotransferase (ALT, SGPT)
Chloride (CL)	Aspartate aminotransferase (AST, SGOT)
Bicarbonate (BICARB)	Calcium corrected
Glucose (GLUC)	Phosphate (PHOS)
Urea	Lactate dehydrogenase (LDH)
Creatinine (CREAT)	Magnesium (Screening only)
Urate	Cholesterol (Screening only)
Albumin (ALB)	Triglycerides (Screening only)
Globulin	HDL (Screening only)
Total protein	Estimated glomerular filtration rate (eGFR)
Total bilirubin (BILI)	C-Reactive Protein (CRP) Not included at Screening
Direct (conjugated) bilirubin (BILDIR)	

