### Treatment and observation

The following procedures will occur during treatment and observation:

1. Administer the appropriate doses of OZ439 and PQP to fasted (8 hours) subjects under direct observation as described in (Section 6.1.5)
2. Follow up subjects as inpatients for 72 hours to monitor safety and tolerability of the treatment and adequate clinical response.
3. Perform symptom-directed physical examination when signs or symptoms of malaria are identified and it is clinically indicated.
4. Obtain 12-lead ECG in triplicate at 4, 6, 8, 12, 24 and 72 (D4) hours post-OZ439 and PQP administration
5. Record vital signs 3 times a day whilst confined.
6. Record malaria clinical score 3 times a day whilst confined.
7. Collect blood samples for malaria 18S qPCR following treatment at 4, 8, 12, 16, 20, 24, 30, 36, 42, 48, 60, and 72 hours post-OZ439 and PQP administration as per allowed time windows
8. Collect blood samples for PK analysis of OZ439 and PQP at 0.5, 1, 2, 3, 4, 5, 6, 8, 12, 16, 24, 48, and 72 hours post-OZ439 and PQP administration as per allowed time windows
9. Collect optional blood samples for complement regulatory proteins (if consented separately) at approximately 48 hours post-OZ439 and PQP treatment.
10. Record AEs and use of concomitant medications.

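### Creatine kinase, the most frequent AE in the Phase IIa OZ439 monotherapy study, is not in the scheduled safety panel, so symptom-free rises would not be systematically ascertained

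*Protocol*

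**What the plan says.** **The signal.** Protocol section 2.3.1 (OZ439 risks) describes a Phase IIa monotherapy study in malaria patients at 200 to 1200 mg, in which "increased blood creatine phosphokinase was the most frequently reported AE". The same sentence continues that "a dose relationship was not seen for this AE and no clinically relevant muscular AEs were reported".

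**The panel.** Protocol section 7.2.1, under "Biochemistry and CRP biomarker", lists the scheduled analytes. They include ALT, AST, ALP, total and direct bilirubin, LDH, urate and creatinine. CK is not listed.

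**The objective.** Primary objective (b) is safety and tolerability. Its endpoint in section 4.2.1 is the incidence, severity and relationship of AEs.

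**Posture (secondary).** Section 2.3.1 also reports two individual cases involving orthostatic hypotension. On the first: "One case of vasovagal syncope considered related to therapy was reported in association with sinus arrest and orthostatic hypotension". On the second, a possibly related atrial fibrillation after OZ439 plus ferroquine: "The event occurred in context of symptomatic orthostatic hypotension and resolved spontaneously without medical treatment". Supine and standing readings are taken at screening. Thereafter, according to section 7.1.1, "At all other time points, vital signs will be measured after the subject has rested in the seated position". In confinement the instruction is "Record vital signs 3 times a day whilst confined". SAP section 6.8 describes the collected heart rate and blood pressure as supine.

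**The concern.** A laboratory AE exists in the data only if someone runs the assay. The protocol names a laboratory abnormality as the leading AE of one of its two study drugs in an earlier monotherapy study, and then leaves that analyte out of a fairly broad panel without giving a reason. A study report with no CK events would reflect the absence of measurement, but could be read as reassurance on a primary objective.

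There is also an interpretive cost. AST alone can trigger a hepatic AESI. CK is the analyte that would speak directly to a muscle contribution, and it would be missing at the moment of attribution.

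**Working it through.** No figure in the plan is in dispute, so the check is a reading and a count.

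**1. Is CK scheduled anywhere?**

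| Place | CK present? |
|---|---|
| Protocol 7.2.1 biochemistry list (25 items) | No |
| Protocol 7.3.1 to 7.3.4 visit procedures and 7.3.7 schedule | No; they call for biochemistry as a panel |
| Protocol 8.1.3 and SAP 6.8 AESI criteria | No |
| Protocol Appendix 2 blood volumes | No separate line |
| SAP 6.8 laboratory elevation categories | No; ALT, AST and bilirubin only |
| SAP Tables 14.3.4.2a/b and 14.3.4.4a/b | Defined by panel, so they inherit the omission |

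**2. How many samples could carry it?** The visit procedures call for biochemistry at screening, the eligibility visit, Day 8 admission, 72 h, 336 h, 504 h and 672 h after dosing, before Riamet, and end of study. That is 9. Appendix 2 gives 6 samples of 5 mL and 3 of 8.5 mL, and 6 + 3 = 9, which agrees. Three precede dosing and six follow it. The eligibility sample is waived if screening bloods fall in its window, and an early Riamet course adds one follow-up sample. Scheduled CK results are 0 of 9 per subject, for all 24 subjects.

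**3. Can a rise reach the tables without an assay?** Under section 8.1.1 an abnormal result becomes an AE only if it meets stated criteria, such as symptoms, further testing or clinical significance. Other abnormal results are analysed separately as laboratory data. Both routes need a measured value. A symptom-free rise prompts no test, so it reaches neither.

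**4. What of a CK ordered at discretion?** Section 7.1.1 allows unscheduled safety tests. No CK is planned before inoculation or before dosing, so neither of the two baselines in SAP section 6.1 would exist for it. Safety serum is stored at Day 0 and end of study. The Day 0 tube might supply a retrospective value, but neither document plans that or says whether CK could be measured in it.

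**5. What follows for hepatic AESIs?** Section 8.1.3 has four hepatic triggers. Three can be met on AST without ALT: above 5xULN; above 2xULN with raised bilirubin or INR; and above 2xULN with symptoms. Fatigue, nausea, vomiting and fever count for the last of these, and Appendix 3 lists all four as signs or symptoms of malaria. A mildly raised AST in a subject with malaria symptoms can therefore qualify, and no muscle marker is available to help explain it.

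**6. Posture.** There is one visit with a supine-to-standing reading (screening) and none after it. The later posture is seated in the protocol and supine in the SAP. Neither shows a postural fall.

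**The case against.** The case on the other side is substantial.

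- **The CK finding is qualified.** It came from malaria patients, showed no dose relationship and had no clinically relevant muscular events. Section 2.3.1 says gastrointestinal events were the most frequent in healthy subjects, and that malaria and QTc prolongation were the most frequent in the Phase IIb study of this combination. This stands and limits the clinical weight. It does not make incidence measurable, and the same section calls the healthy-subject AE profile similar to that in patients.
- **Other effects are highlighted more strongly.** A reader might infer that CK and orthostatic hypotension are the two OZ439 effects the protocol singles out. They are not. Section 2.3.1 also covers gastrointestinal, liver, haematological, QTc and rhythm effects. It asks for close monitoring of liver and cardiac function, and the plan provides both.
- **Other routes to detection exist.** A reader might infer that these effects cannot be detected at all. That goes too far. AEs are observed and elicited, and unscheduled tests are allowed. What is missing is systematic ascertainment.
- **AST can be partly interpreted.** ALT, ALP, bilirubin and LDH come from the same sample, and section 2.3.1 reports an independent review attributing earlier liver-test rises in this model most likely to malaria. It would be wrong to say that a liver and a muscle origin cannot be separated; the judgement is harder.
- **The orthostatic cases were clinically apparent.** Such events would be caught by 72 hours of inpatient observation, the post-dose ECGs, the malaria clinical score (which includes hypotension) and AE collection. Nor are vital signs untied to dosing: section 7.1.1 gives tolerance windows by hours after dosing. This half does not carry the point.
- **Unseen documents.** Section 8.1 defers safety monitoring detail to a safety management plan, which might add CK. That cannot be checked here.

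**Conclusion.** The point holds for CK in a limited form. The protocol reports a CK rise as the leading AE of an earlier OZ439 study, and neither document schedules the assay at any of the nine nominal biochemistry samples. Symptom-free rises would not be systematically ascertained, a discretionary value would lack a scheduled baseline, and AST-triggered AESIs would be harder to interpret. An absence of CK events in the report could not be read as zero incidence.

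The size in missed cases cannot be given. The documents state no CK rate, and an expected count among 24 subjects would rest on an invented one. The conclusion does not depend on a rate. It does assume that no document outside these two adds CK.

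On posture, only two things stand. Symptom-free postural falls after screening would not be systematically seen, and the seated and supine descriptions conflict. Whether a standing test is worth adding is a matter on which reasonable reviewers could differ.

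**What to change.** **Protocol.** For any subject still to be dosed, add CK to the biochemistry list in section 7.2.1 at the existing baseline and post-dose time points. If the sponsor prefers not to, state why it is unnecessary. Sampling before inoculation and at Day 8 admission would supply both SAP baselines.

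**SAP.** Name CK in Tables 14.3.4.2a/b and 14.3.4.4a/b.

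**Subjects already dosed.** SAP sections 2.1 and 2.4 describe the three cohorts and 24 subjects in the past tense, so this may be the only part still open. State in the SAP and CSR that CK was not assessed, so that no CK events is not reported as none occurring.

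**Secondary.** Reconcile the posture for post-screening vital signs between protocol section 7.1.1 and SAP section 6.8. State that postural change was assessed at screening only.

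**Cost.** One analyte on samples already taken, with no extra draw or visit, provided the laboratory can run it on the same tube. Some exercise-related CK rises will be recorded; the pre-dose values help in judging them. The first post-dose biochemistry is at 72 h, so a rise that resolved before then would still be missed. The statement for subjects already dosed costs a sentence in each document.

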#### Piperaquine phosphate (PQP) risks

PQP as a combination antimalarial with hydroartemisinin is well tolerated in both adults and children, with the main AEs reported being GI disturbances such as diarrhea [39, 40]. Studies with dihydroartemisinin/PQP demonstrated corrected QT (QTc) interval prolongation during treatment [41, 42]. Very few individual patients have been observed to have a prolongation that could be regarded as clinically significant (>60 msec); of note, the QTc prolongation induced by PQP has not been reported to be associated with clinically relevant cardiovascular events, would suggest a lack of pro-arrhythmic effect. Therefore, although statistically significant, the QTc prolongation observed following PQP therapy is unlikely to be of clinical concern. European regulatory authorities have advised that Eurartesim (dihydroartemisinin/PQP) not be administered with food to reduce PQP peak concentrations, and caution that pre- and post-electrocardiographic monitoring be undertaken, and avoidance of concomitant recent exposure to drugs at risk of QTc prolongation [18, 42, 43]. Therefore, during this study, subjects will receive PQP under fasting conditions and will have ECGs recorded before and after treatment.

PQP has been clinically well tolerated in previous IBSM studies using this drug [14]. In these studies, PQP treatment demonstrated a robust safety profile in doses up to 960 mg when used for the treatment of uncomplicated falciparum malaria infection.

Details on the safety and efficacy of PQP as part of the combination product Eufartesimbe found in the European Medicines Agency (EMA) European Public Assessment Report.

### Rescue Medication risks

Riamet®, Primacin™ and Artesunate risks are detailed in their respective approved manufacturer's prescribing information (Appendix 1). Primacin™ may cause severe haemolytic anaemia in subjects with glucose-6-phosphate dehydrogenase (G6PD) deficiency. Subjects will be tested for G6PD deficiency at screening to ensure the safety of Primacin™. The G6PD status will determine how the subject is treated with Primacin™.

### General risk management

The risk to subjects in this study will also be minimised as follows:

- Adherence to the inclusion/exclusion criteria to ensure that only subjects who are any perceived risk are enrolled in the study
- Close clinical and laboratory monitoring to ensure the safety and wellbeing of the subjects.
- Subjects will be prescribed curative therapy for malaria (Riamet® with the addition of Primacin™ if required) for final parasite clearance during or at the end of the study
- The total volume of blood drawn from each subject enrolled into the study (including optional exploratory research sampling) will not exceed a standard unit of blood (approximately 450 mL) over any 30 day period.
- In the rare event that a subject requires hospitalisation at the request of the Principal Investigator or his representative, this will be done at the Infectious Diseases Unit, Royal Brisbane and Women's Hospital. Emergency procedures are in place at the Q-Pharm clinics for dealing with any unforeseen clinical emergencies which may arise.

With these safety provisions, the overall risk to the subjects in the study is considered to be minimal and acceptable, and the potential of future improved treatment for malaria is considered to outweigh these potential risks.

---

